13.	Vulnerable Populations	21
14.	Local Number of Participants	21
15.	Recruitment Methods.....	21
16.	Withdrawal of Participants	22
17.	Risk to Participants	23
18.	Potential Benefits to Participants	24
19.	Compensation to Participants	24
20.	Data Management and Confidentiality	25
21.	Plans to Monitor the Data to Ensure Safety of Participants and Data Integrity	27
22.	Provisions to Protect the Privacy Interest of Participants	30
23.	Economic Burden to Participants	31
24.	Informed Consent	31
25.	Setting.....	32
26.	Resources Available	32
27.	References	32
28.	Protocol Checklist	35

1. Study Summary

Project Title	Treatment of Long COVID (TLC) Feasibility Trial: Feasibility Assessment of a Decentralized Platform Double-Blind, Randomized Controlled Trial Investigating Repurposed Drugs in the Treatment of Post-Acute Sequelae of Coronavirus-19 (PASC)																						
Project Design	Fully decentralized single center, double-blind, randomized, placebo-controlled pilot feasibility trial																						
Primary Objective	Assess the feasibility and acceptability of methods and procedures, as determined by subjects, to be employed in a larger scale decentralized platform adaptive randomization clinical trial.																						
Secondary Objective(s)	
Completion rate of quality of life assessmentsAdherence to Investigational ProductAttrition ratesSafety																						
Exploratory Objectives	
Efficacy																						
Research Intervention(s)/Interactions	
CetirizineFamotidine																						
Study Population	Adults ≥18 years of age with new or worsened symptoms since onset of COVID-19 that are persistent at the time of enrollment and have lasted for ≥ 12 weeks (including at least one of the following: fatigue, post-exertional malaise (PEM), headache, brain fog, sleep disturbance, dysautonomia). All subjects will be Georgia residents.																						
Sample Size	Up to 36																						
Study Duration for individual participants	16 weeks (4 weeks Screening, 12 weeks Treatment)																						
Study Specific Abbreviations/ Definitions	

AE	Adverse event	

COVID-19	Disease caused by SARS-CoV-2	

CRC	Clinical Research Coordinator	

EMR	Electronic Medical Record	

GAD-7	Generalized Anxiety Disorder 7-question Survey	

HRA	Histamine Receptor Antagonist	

IP	Investigational product	

ITT	Intent-to-treat	

ME/CFS	Myalgic Encephalomyelitis/Chronic Fatigue Syndrome	

MFIS	Modified Fatigue Impact Scale	

PASC	Post-acute Sequelae of SARS-CoV-2	

	AE	Adverse event	COVID-19	Disease caused by SARS-CoV-2	CRC	Clinical Research Coordinator	EMR	Electronic Medical Record	GAD-7	Generalized Anxiety Disorder 7-question Survey	HRA	Histamine Receptor Antagonist	IP	Investigational product	ITT	Intent-to-treat	ME/CFS	Myalgic Encephalomyelitis/Chronic Fatigue Syndrome	MFIS	Modified Fatigue Impact Scale	PASC	Post-acute Sequelae of SARS-CoV-2
AE	Adverse event																						
COVID-19	Disease caused by SARS-CoV-2																						
CRC	Clinical Research Coordinator																						
EMR	Electronic Medical Record																						
GAD-7	Generalized Anxiety Disorder 7-question Survey																						
HRA	Histamine Receptor Antagonist																						
IP	Investigational product																						
ITT	Intent-to-treat																						
ME/CFS	Myalgic Encephalomyelitis/Chronic Fatigue Syndrome																						
MFIS	Modified Fatigue Impact Scale																						
PASC	Post-acute Sequelae of SARS-CoV-2																						

	PHQ-8	Patient Health Questionnaire 8-question survey
	POTS	Postural Orthostatic Tachycardia Syndrome
	PP	Per protocol
	PROMIS	Patient Reported Outcome Measurement Information System
	RC	Research coordinator
	WHODAS	Mean WHO Disability Assessment Schedule
Funding Source (if any)	Office of the Assistant Secretary for Planning and Evaluation (ASPE) and Emory University.	

2. Objectives

Primary Objective: The primary objective is to assess the feasibility and acceptability of methods and procedures, as determined by subjects, to be employed in a larger scale decentralized platform adaptive randomized clinical trial.

Secondary Objectives: Secondary objectives are to assess completion rate of quality of life assessments, adherence to Investigational Product, attrition rates and safety.

Exploratory Objective: The exploratory objective is to assess efficacy of histamine receptor antagonist (HRA) therapy in improving outcomes in patients with Post-Acute Sequelae of Coronavirus-19 (PASC) and at least one of the following symptoms: fatigue, post-exertional malaise (PEM), headache, brain fog, sleep disturbance, dysautonomia.

3. Background

In December 2019, a new human coronavirus with respiratory tropism, SARS-CoV-2, emerged in China and rapidly spread to other parts of the world [6, 7]. The coronavirus disease 2019 (COVID-19) has resulted in over 100 million confirmed cases of infection [8]. Although there are numerous publications describing the wide range of acute phase manifestations, there remains limited data on long-term sequelae of COVID-19, aka Post-Acute Sequelae of SARS-CoV-2 (PASC) or “Long COVID”. PASC may occur in 20-30% of COVID-19 patients, and symptoms result in significant impairments in quality of life [9-18]. With the growing prevalence of COVID-19, PASC is creating a substantial global burden [19]. Though common complaints include dyspnea, fatigue, brain fog, weakness, pain syndromes, anxiety, and depression, PASC can manifest as a myriad of symptoms [10, 11, 13]. In many, these symptoms can persist for >6 months, and the true duration of this disease remains unclear [13].

Though the underlying pathophysiology of PASC symptoms remains unknown, several mechanisms have been proposed in individuals with no detectable parenchymal or structural damage resulting from acute COVID-19 infection. SARS-CoV-2 can persist in bodily

fluids for a prolonged period extending beyond the acute viral phase, but little is known about the clinical relevance of this finding [20,21]. Concern exists that persistent viral reservoirs remain undetected, promoting ongoing, heightened immune responses contributing to the myriad of symptoms seen in PASC [22]. Furthermore, natural killer (NK) cells appear to play an important role in the innate immune response to COVID-19, wherein diminished NK cell response is associated with viral persistence and increased mortality [23]. Reduction in NK cell number and function occurring in COVID-19, particularly severe infections, results in decreased clearance of infected cells and unchecked elevation of tissue-damaging inflammation markers. SARS-CoV-2 infection skews the immune response towards an overwhelmingly inflammatory phenotype. Restoration of NK cell effector function has the potential to correct the delicate immune balance required to effectively overcome SARS-CoV-2 infection [24]. Others suggest that PASC is mediated through non-viral inflammatory mechanisms, such as mast cell activation syndrome (MCAS), which may explain the inflammatory, multisystem nature of PASC symptoms [25]. Here it is posited that a dysfunctional population of mast cells become hyper-stimulated in a continuous activation loop, leading to the heterogeneous clinical presentations seen in PASC patients. Also proposed is an autoimmune link, wherein hosts lose tolerance to auto antigens due to molecular mimicry between pathogen and host proteins leading to dysregulated immune response. Autoantibodies opposing B cells, various cytokines, and cellular membrane components have been identified in patients with severe acute COVID-19, though studies demonstrating this processing in PASC remain sparse [26-28].

A host of medications have been investigated in the treatment of acute COVID-19, though few drugs have been studied in formal randomized controlled trials in the post-acute phase to address persistent symptoms and long-term sequelae. A panel assembled by the CURE Drug Repurposing Collaboratory (CDRC) – a public-private partnership - that includes at least one of each of the following—physician, pharmaceutical engineer, pharmacist, public health professional, immunologist, patient, and drug repurposing expert—reviewed the available data for over 60 candidate therapeutic approaches. Several drugs appeared to be promising based on early anecdotal reports and plausible mechanisms. Given the urgency of finding answers and the need for randomized controlled trials to begin to determine drugs that are effective for PASC, the panel selected the following treatment as an initial approach.

As mast cell activation syndrome is one theorized mechanism of severe acute COVID-19 and a proposed physiologic derangement contributing to PASC, histamine receptor antagonists (HRA), such as famotidine and cetirizine, have garnered interest as possible drug candidates. (See section 5.1.2). These agents may modulate their effects through reductions in cellular inflammatory mediators, such as histamine, serotonin, TGFb, VEGF, IL6, IL8,

interferons, and NETs and modulation of dysregulated T cells. Administration of HRAs in a relatively small cohort of PASC patients (N=25) demonstrated a 72% improvement in patient reported symptoms, of which, 20% had complete symptom resolution [34]. This is compared with those who received no treatment (N=40) who experienced a 50% improvement, with complete resolution in 4% in the same period.

4. Study Endpoints

Primary endpoint:

- Subject reported (patient reported outcome [PRO]) end of study questionnaire

Secondary endpoints:

- % subjects who complete 70% of PRO surveys/questionnaires at 12 weeks
- % subjects who complete 70% of IP doses through 12 weeks
- % subjects Lost to Follow Up (LTFU)
- % subjects voluntarily terminate participation
- Incidence of adverse events and serious adverse events
- Number of discontinuations or temporary suspensions of IP

5. Study Intervention/Investigational Agent

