6.2 Study Schema

6.3 PRO Collection—Feasibility and Efficacy Assessments

Subjects will complete the following PROs at protocol specified timepoints as described in Section 6.5 and as detailed in the Schedule of Events in Section 6.7. Subjects with difficulty completing the PROs in Emory's Part 11 compliant REDCap instance will be contacted by CRC via telemedicine or telephone. In these encounters, CRC will administer PRO surveys and collect symptom tracking data at protocol designated study time points.

- **PROMIS Fatigue 7A**—measures fatigue with daily activities
- **Insomnia Severity Scale**—measures difficulty sleeping
- **PROMIS Cognitive 6A**—measures difficulty thinking and concentrating
- **DePaul Symptom Questionnaire (DSQ-1) Short form**—measures post-exertional malaise
- **COMPASS 31**—measures symptoms of dysautonomia

- **WHO Disability Assessment Schedule (WHODAS 2.0)**—measures health and disability
- **Headache Diary**—measures the number and severity of headaches (completed daily during the 7 days prior to study visit)
- **Self-reported Persistent Symptoms Survey**—measures presence or absence of Long COVID symptoms and their severity
- **Concomitant Medications Log**—records subject-reported medications, supplements and vitamins
- **Self-reported Changes to Health Log**—records subject-reported adverse events
- **IP Adherence Log**—records subject-reported adherence to IP dosing regimen
- **End of Study Survey**—assesses the feasibility and acceptability of methods and procedures

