6.5 Detailed Study Procedures and Assessments by Study Period/Study Day

The procedures performed during this study will be performed according to this section and the Schedule of Events table shown in Section 6.7 below.

6.5.1 Screening (Within 28 days ± 3 days of Day 0):

Prior to any study-specific procedures or data collection, the CRC will obtain informed consent from potentially eligible subjects. If the subject is not an Emory patient, the subject will be asked to sign a medical release form. Using a verbal consent, subjects will be prescreened by televisit by the CRC who will review the inclusion/exclusion criteria. Subjects who remain interested and are potentially eligible will then be consented, and medical records will be sought from the subject's healthcare system to confirm eligibility.

The following procedures and data collection will be performed during Screening:

- Signature of electronic Informed Consent Form and provision of subject information

- Collection of sociodemographic data
- Medical record review
- Collection of medical and surgical history, including acute COVID-19 history, PASC history (time from symptom onset or positive SARS-CoV-2 testing), and COVID-19 vaccination status
- Assessment routine concomitant medications
- Assessment of baseline PROs:
 - WHODAS 2.0 36-item score
 - PROMIS Fatigue 7a
 - Insomnia Severity Index
 - PROMIS Cognitive Function Short Form 6A
 - DSQ-PEM Short Form
 - Headache Diary (completed daily during the 7 days prior to visit)
 - COMPASS 31
- Confirm Inclusion and Exclusion criteria

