6.5.4 Days 2-84: Participant takes IP daily

6.5.5 Weekly: Participant completes adverse event log, study medication adherence log, concomitant medication log, self-reported persistent symptoms questionnaire

6.5.6 Days 42, 63, and 84, all +/- 3 days, subjects enter patient reported outcome (PRO) data into REDCap.

- PRO data to be collected
 - WHODAS 2.0 36-item score
 - PROMIS Fatigue 7a
 - Insomnia Severity Index
 - PROMIS Cognitive Function Short Form 6A
 - DSQ-PEM Short Form
 - Headache Diary (completed daily during the 7 days prior to visit)
 - COMPASS 31

6.5.7 Day 84/End of Study (EOS) or Early Termination: Participants complete End of Study survey

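### Must the plan spell out which visits count towards the 70% PRO survey completion rate?

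*Combined protocol and SAP*

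**What the plan says.** Section 4 lists two neighbouring secondary endpoints: the percentage of "subjects who complete 70% of PRO surveys/questionnaires at 12 weeks" and the percentage of "subjects who complete 70% of IP doses through 12 weeks". Section 7.4.1 (Attrition) repeats both with the same prepositions, *at* for surveys and *through* for doses, and adds no list of forms or visits. The related secondary objective in section 2 is "to assess completion rate of quality of life assessments".

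The schedule itself is clear. Section 6.5.1 lists seven instruments under "Assessment of baseline PROs", and section 6.5.6 repeats the same seven: "Days 42, 63, and 84, all +/- 3 days, subjects enter patient reported outcome (PRO) data into REDCap". Section 7.5.1 names those seven again, at Weeks 6, 9 and 12.

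Elsewhere the label PRO is used more loosely. Section 4 describes the primary endpoint as "Subject reported (patient reported outcome [PRO]) end of study questionnaire". Section 6.3 opens with "Subjects will complete the following PROs at protocol specified timepoints as described in Section 6.5" and then lists twelve items, including the weekly logs, the symptom survey and the End of Study Survey. Section 6.5.5 calls the weekly symptom form a "self-reported persistent symptoms questionnaire".

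**The concern.** A percentage needs a denominator, and this one can be read in at least three ways: the Day 84 set only (the literal sense of *at*), the three follow-up visits together, or those visits plus screening. With three equal follow-up visits, the 70% cut lies just above two thirds, so one missed visit is enough to decide the result. The same subject can then be a success on one reading and a failure on another.

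This is a feasibility trial, and the rate is the only endpoint that measures the secondary objective on completing quality-of-life assessments. If the denominator were chosen after the data had been seen, the more flattering figure could be reported. A strict Day 84 reading would also ignore two of the three follow-up visits.

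**Working it through.** The plan gives no expected completion rate or sample-size calculation for this endpoint, so there is no stated figure to reproduce. The check is a direct count.

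**Inputs.** Seven instruments (sections 6.5.1, 6.5.6, 7.5.1); three follow-up visits, Days 42, 63 and 84 (section 6.5.6); one screening set (section 6.5.1); cut 70% (section 4). Each visit's headache diary counts as one form.

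**Forms due and forms needed.**
- Day 84 only: 7 due; 0.7 × 7 = 4.9, so 5 needed.
- Days 42, 63 and 84: 7 × 3 = 21 due; 0.7 × 21 = 14.7, so 15 needed.
- With screening: 7 × 4 = 28 due; 0.7 × 28 = 19.6, so 20 needed.

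**Every whole-visit pattern, screening complete.**

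| Visits completed | 21 forms | 28 forms | Day 84 only |
|---|---|---|---|
| 42, 63, 84 | 21/21 pass | 28/28 pass | 7/7 pass |
| 42, 63 | 14/21 fail | 21/28 pass | 0/7 fail |
| 42 | 7/21 fail | 14/28 fail | 0/7 fail |
| none | 0/21 fail | 7/28 fail | 0/7 fail |
| 63, 84 | 14/21 fail | 21/28 pass | 7/7 pass |
| 42, 84 | 14/21 fail | 21/28 pass | 7/7 pass |
| 84 | 7/21 fail | 14/28 fail | 7/7 pass |
| 63 | 7/21 fail | 14/28 fail | 0/7 fail |

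The first four rows are full completion and plain dropout. In them the 21-form and Day 84 columns agree throughout, and only the 28-form column departs, in one row. The last four rows are intermittent misses. The 21-form and Day 84 readings differ in three of these, always because Day 84 was completed after an earlier miss.

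**How plausible is the 28-form reading?** Section 7.4.1 places the rate under Attrition, meaning loss during the study. The screening forms come before randomization, and section 19 makes completing them part of completing the Screening Phase. Among randomized subjects they would be close to constant and would add little beyond seven near-certain passes.

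**How large could the differences be?** The documents give no missed-visit rate, so the rates here are assumptions.
- Independent whole-visit misses at rate m: (1−m)³ on 21 forms, (1−m)³ + 3m(1−m)² on 28, and 1−m on Day 84. At m = 0.05: 85.7%, 99.3%, 95.0%. At m = 0.10: 72.9%, 97.2%, 90.0%.
- Dropout at rate d before each visit: (1−d)³ on 21 forms and on Day 84, and (1−d)² on 28. The 28-form figure is higher by d(1−d)²: 4.5 points at d = 0.05 and 8.1 at d = 0.10.

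Dropout of 10% before each visit loses 1 − 0.9³ = 27.1% by Day 84. Section 14 goes from about 36 to 24, an allowance of 12/36 = 33.3% that must cover screen failure as well. Heavier dropout would strain the plan's own assumptions.

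**Per subject.** With the 24 of section 14, one subject is 1/24 = 4.2 points.

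**The case for a change.** The strongest case for a change is that the *at* and *through* contrast appears in both section 4 and section 7.4.1, so it is hard to dismiss as a slip. Even a cumulative reading leaves 21 against 28 forms open. If misses were intermittent and independent at 10%, the Day 84 and 21-form figures would stand 90.0 − 72.9 = 17.1 points apart, or about four subjects in 24. A wider list of PROs blurs matters further. Assuming 12 weekly entries, adding the symptom survey and the End of Study Survey gives the one-missed-visit subject 27/34 = 79.4%, and adding the three weekly logs gives 63/70 = 90.0%. Sections 4 and 7.4.1 also name no analysis population for the rate.

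It stands that the wording is incomplete. It is not contradictory, because the two sections match each other word for word on this point. The other parts weaken on inspection:
- **Intermittent misses.** A subject would have to skip all seven instruments at one visit and then return. Coordinators can administer the forms by telephone or televisit (section 6.3), overdue subjects are reminded (section 6.6), a stipend is tied to each of the three visits (section 19), and late data are pursued (section 20.4).
- **Which forms.** The objective speaks of quality-of-life assessments, and sections 6.5.1, 6.5.6 and 7.5.1 all give the same seven instruments. Section 6.3 itself separates PRO surveys from symptom tracking when it describes coordinator help. The adherence and health-change logs supply other secondary endpoints.
- **Late forms and population.** Section 20.4 keeps everything collected before loss to follow-up or withdrawal of consent, which points to counting late forms. In section 7.2 the ITT and Safety sets have the same members, so an overall rate is identical in both. A per-protocol set would be an odd base for attrition.

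**Conclusion.** No change is needed. The denominator is not stated, but the plan contains what an analyst needs to choose one sensibly: the seven instruments due at Days 42, 63 and 84, among all subjects who took study product, with the choice stated beside the table. The most striking split, 66.7% against 75.0%, requires counting screening forms in an attrition measure. Without them, only subjects who miss an earlier visit and complete Day 84 are classified differently, at 4.2 points each with 24 subjects.

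The consequence is small because the rate is descriptive. No test, success threshold or decision about the larger trial rests on it. Section 7.1 calls for a review of missing-data patterns, and section 7.5.1 tabulates each instrument at Weeks 6, 9 and 12, so completion by visit is visible on any reading and every version can be recomputed from the same data. This assumes that whole-visit intermittent misses are uncommon. If they proved frequent, the by-visit tables would show it.

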5.1 Cetirizine

Cetirizine is a histamine receptor antagonist (HRA). It will be dispensed as a 10mg capsule with instructions for subjects to take one capsule daily by mouth. Subjects will be instructed to take the IP as close to the same time every day as possible, preferably at bedtime.

5.2 Famotidine

Famotidine is a histamine receptor antagonist (HRA). It will be dispensed in 20mg capsules with instructions for subjects to take one capsule twice daily, as close to the same time every day as possible.

5.4 Pharmacokinetics

5.4.1 Cetirizine

Cetirizine hydrochloride is a second-generation antihistamine that selectively antagonizes peripheral histamine (H1) receptors [34]. Glomerular filtration is the predominant mode of renal elimination for the predominately unmetabolized drug, which has minimal liver metabolism or CYP450 interaction. The half-life is

8.3 hours with preserved renal function and 24.9 hours with moderate to severe renal impairment.

5.4.2 Famotidine

Famotidine hydrochloride selectively antagonizes peripheral histamine (H₂) receptors [33]. Glomerular filtration is the predominant mode of renal elimination for the predominately unmetabolized drug, which has minimal liver metabolism or CYP450 interaction. The half-life is 2.5 hours with preserved renal function and 20 hours with severe renal impairment.

5.5 Placebo

The investigational pharmacy will provide placebo capsules manufactured to match each study treatment for oral administration.

The HRA placebos will be designed as capsules of the inert substance microcrystalline cellulose and will match the morphology of the respective HRA treatment capsules.

5.6 Storage and Stability

All IP will be stored at USP controlled room temperature 20°-25° (68°-77 °F). Excursions between 15° and 30° (59° and 86 °F) that are experienced in pharmacies, hospitals, and warehouses, and during shipping are allowed. Provided the mean kinetic temperature does not exceed 25°, transient spikes up to 40° are permitted as long as they do not exceed 24 h. Participants will be instructed to maintain their IP under these conditions. IPs will be maintained in a tight, child-proof container.

Control of the IPs used in this protocol will be accomplished by following the established, approved organizational SOPs of the Emory Investigational Drug Service (IDS) regarding protocol management and IP accountability, IP storage, temperature monitoring, randomization by unblinded pharmacists, dose preparation, IP labeling, and shipping of study medication to subjects.

